4.2. Study Endpoints

4.2.1. Primary Endpoint

This study's primary endpoint is time to fusion at post-operative follow-up, evaluated by radiologist interpretation of radiographic and CT imaging.

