9.3. Description of Statistical Methods

9.3.1. Analysis of the Primary Efficacy Endpoint(s)

The primary endpoint analysis involves a comparison of participant fusion rates at 6-weeks, 3-months, 6-months and 12-months after surgical intervention. All participants who were enrolled will be included in this analysis. Participants will be excluded from the analysis if a CT scan and x-ray cannot be obtained at the 6-week visit.

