9.4.4. Missing Data

In evaluating primary endpoints, missing radiographic data will be excluded from the analysis. If 6-week radiographic endpoints cannot be obtained, the participant will be removed from the study.

In evaluating secondary endpoints, the following methods will be followed for including missing endpoint values

- Last observation carried forward
- All missing data are worst possible response
- All missing data are best possible response

10. Source Documents and Access to Source Data/Documents

Source data are all information, original records of clinical findings, observations, or other activities in a clinical trial necessary for the reconstruction and evaluation of the trial. Examples of these original documents and data records include, but are not limited to, hospital records, clinical and office charts, laboratory notes, memoranda, participant' memory aids or evaluation checklists, pharmacy dispensing records, recorded audio tapes of counseling sessions, recorded data from automated instruments, copies or transcriptions certified after verification as being accurate and complete, microfiches, photographic negatives, microfilm or magnetic media, x-rays, and participant files and records kept at the pharmacy, at the laboratories, and medico-technical departments involved in the clinical trial. It is acceptable to use CRFs as source documents. If this is the case, it should be stated in this section what data will be collected on CRFs and what data will be collected from other sources.

11. Quality Assurance and Quality Control

The study team will follow SOPs on data entry and storage. Any missing data or data anomalies will be communicated to PI for clarification/resolution.

The study team will follow SOPs on staff training requirements, and a training tracking log will be maintained by the Research Coordinator and stored in the study binder.

Following written SOPs and protocol, the monitors will verify that the clinical trial is conducted and data are generated, documented (recorded), and reported in compliance with the protocol, GCP, and the applicable regulatory requirements (e.g., Good Laboratory Practices (GLP)).

The investigational site will provide direct access to all trial related sites, source data/documents, and reports for the purpose of monitoring and auditing by the sponsor, and inspection by local and regulatory authorities.

12. Ethics/Protection of Human Subjects

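### Excluding missing radiographic data (9.4.4) from visit-by-visit fusion rates (9.3.1) discards what a participant's other scans show, and biases the rates if missing a scan is related to fusion

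*Protocol*

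**What the plan says.** Section 4.2.1 of the Protocol defines the outcome as an event time: "This study's primary endpoint is time to fusion at post-operative follow-up". Section 9.3.1 describes the analysis as "a comparison of participant fusion rates at 6-weeks, 3-months, 6-months and 12-months after surgical intervention", and adds: "All participants who were enrolled will be included in this analysis". The only exception it names concerns the 6-week imaging.

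Section 9.4.4 gives two rules for the primary endpoint. The general one is that "missing radiographic data will be excluded from the analysis". The second is specific: "If 6-week radiographic endpoints cannot be obtained, the participant will be removed from the study". Because the 6-week scan has its own rule, the general sentence is what governs the 3-, 6- and 12-month scans.

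For secondary endpoints the same section lists last observation carried forward and worst-case and best-case handling. It lists nothing comparable for the primary endpoint. Section 6.3.5 allows no study imaging at unscheduled visits outside the windows, so such a visit cannot replace a missed scan. Section 5.3 sets the sample at 20.

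**The concern.** When fusion is observed only at scheduled scans, a missed scan widens the interval in which fusion could have happened. It does not cancel what the other scans show. Suppose a participant is read as fused at 3 months and has no 12-month scan. Under 9.4.4 with 9.3.1, that participant leaves both the numerator and the denominator of the 12-month rate. A participant read as not fused at 6 months who then misses 12 months leaves that rate too, although the earlier scans show that fusion had not occurred by 6 months.

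If missing a scan is unrelated to fusion, this costs only precision, which is scarce with 20 participants. If it is related (people who feel well skip a visit, or people who do badly leave), the visit rates are biased. If the relation differs between arms, so is the device comparison.

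**Working it through.** **Inputs.** From the Protocol: 20 participants (5.3); scans at 6 weeks and 3, 6 and 12 months (6.1.1.5); permuted blocks with no stated ratio (9.4.1). Assumed, because the Protocol gives no values: 10 per arm; true cumulative fusion of 10/40/65/80% at the four visits; the 6-week scan always present; the missed-scan rates below. The Protocol gives no alpha, power, effect size or missed-scan rate with the sample of 20, so there is no stated figure to reproduce.

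**1. Will the rule be used?** The chance of at least one missed scan among 20 at a given visit is 1 − (1 − d)^20. For d = 5, 10, 15 and 20% this is 64, 88, 96 and 99%.

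**2. Small-sample arithmetic.** Take one arm with 6/10 = 60% truly fused at 6 months.
- Two participants already read as fused at 3 months miss the scan: exclusion gives 4/8 = 50%. Using their 3-month scans gives 6/10 = 60%.
- Two unfused participants miss it instead: exclusion gives 6/8 = 75%.

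So two missed scans can put the rate at 50% or 75% with no change in the truth. These are illustrations, not expected effects.

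**3. Expected size at 12 months.** Let f be the chance that a participant already read as fused misses a later scan, and u the chance for everyone else. The share read as fused by 6 months is

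S = 0.10 + 0.30(1 − u²) + 0.25(1 − u).

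The 12-month rate under exclusion is

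[S(1 − f) + (0.80 − S)(1 − u)] / [S(1 − f) + (1 − S)(1 − u)].

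For f = 0.30 and u = 0.05: S = 0.10 + 0.2993 + 0.2375 = 0.6368, and the rate is (0.4458 + 0.1550)/(0.4458 + 0.3450) = 0.6008/0.7908 = 76.0%, against a true 80%.

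If missingness depends instead on true fusion status at that visit, known or not, the rate under exclusion is 0.80(1 − f)/[0.80(1 − f) + 0.20(1 − u)].

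The last column is the interval-censored maximum likelihood estimate under that second mechanism, computed over all scan patterns weighted by their probabilities.

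| f / u | Exclusion, missingness depends on earlier readings | Exclusion, depends on true current status | Interval-censored, depends on true current status |
|---|---|---|---|
| 10% / 5% | 79.3% | 79.1% | 79.5% |
| 5% / 10% | 80.7% | 80.9% | 80.5% |
| 30% / 5% | 76.0% | 74.7% | 76.7% |
| 40% / 5% | 73.9% | 71.6% | 74.7% |
| 5% / 30% | 83.3% | 84.4% | 82.9% |
| 5% / 40% | 84.5% | 86.4% | 84.3% |
| 15% / 15% | 80.0% | 80.0% | 80.0% |

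When missingness depends on earlier readings, the interval-censored estimate is 80.0% in every row.

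**4. A half-fix is not enough.** Suppose participants already read as fused are carried forward while unfused participants with a missing scan still drop out. At 15% missingness unrelated to fusion, S = 0.10 + 0.2933 + 0.2125 = 0.6058. The rate is then (0.6058 + 0.1942 × 0.85)/(0.6058 + 0.3942 × 0.85) = 0.7709/0.9409 = 81.9%. Exclusion is unbiased in that setting, so the half-fix is worse.

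**The case against.** **The text does not say that other scans are ignored.** A reader might infer from 9.4.4 that the whole participant is deleted. The sentence speaks of missing data, and a time-to-fusion analysis that dropped only the missing scan would keep a fusion already seen. Section 9.1 also defers detail to a SAP that is not shown. This stands as a limit on the reading. Even so, visit-specific rates are the only primary analysis the Protocol writes down, and under them exclusion has the effect described. The rule is stated, not left open.

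**The effect may be small.** A reader might also infer a false device difference of about 11 points, from opposite 40%/5% patterns in the two arms (84.5% − 73.9% = 10.6). The documents do not support that as an expectation. They give no missed-scan rate, participants are blinded to device (9.4.1), and visits are reminded and paid (5.3). At 10% against 5%, opposite patterns give 80.7% − 79.3% = 1.4 points. With the same pattern and the same true fusion in both arms, no false difference arises.

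**The remedy is not a full cure.** This stands. When missingness depends on current status that no scan has shown, interval censoring removes only part of the bias (76.7% rather than 74.7%, truth 80%).

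**Fusion might not persist.** Several criteria in the radiographic appendix (lucency, fracture, motion) could change on a later scan, and the Protocol does not say that a fused reading is final. Scan-available rates are therefore a reasonable sensitivity analysis.

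**Conclusion.** The concern holds in a limited form. Read with 9.3.1, the general sentence of 9.4.4 most naturally drops a participant from a visit's rate when that scan is missing, whatever other scans show. That sits badly with the endpoint in 4.2.1 and with the all-enrolled statement in 9.3.1. The primary endpoint also has no sensitivity analysis for missing scans, while the secondary endpoints have several.

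Under the assumed fusion curve, and with missingness that depends on earlier readings, the 12-month rate is off by 0.7 points at 10% against 5% missingness. At 30-40% against 5% it is 4.0 to 6.1 points too low or 3.3 to 4.5 points too high, depending on who misses. With missingness unrelated to fusion the bias is zero and the loss is precision alone. The fusion curve, the missed-scan rates and equal allocation are assumptions. The direction of the argument does not depend on them, but the size does. This should be changed, at low cost; it does not by itself invalidate the trial.

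**What to change.** Replace the first sentence of 9.4.4 with:

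> All available scans are used. Time to fusion is interval-censored between the last scan read as not fused and the first scan read as fused; a participant never read as fused is right-censored at the last scan. A missed scan widens the interval and does not remove the participant. Visit-specific fusion rates are read from the interval-censored estimate.

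Point 9.3.1 to this text. The 6-week removal rule is a separate matter; while it stands, limit the new wording to scans after 6 weeks so that the two do not conflict.

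Do not carry forward only participants already read as fused while dropping unfused participants with missing scans, because that pushes the rates up.

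Add as sensitivity analyses (a) scan-available rates at each visit and (b) best-case and worst-case handling of missing scans, which the Protocol already lists for the secondary endpoints. The first shows how much the persistence assumption matters; the second bounds the bias from unseen status that interval censoring cannot remove.

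Cost: wording, slightly more programming, and the explicit assumption that fusion persists once read. No extra scans or participants are needed.

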3.2. Secondary Objective(s)

The secondary objectives of this study are to:

- Compare participants' pre-surgical and post-surgical VAS, ODI, EQ-5D, and SF-36 scores to determine whether treatment with Tritanium or PEEK yields faster pain and quality of life improvement.
- Monitor device safety by gathering adverse event reports

4. Study Design and Endpoints

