4.2.2. Secondary Endpoint(s)

The secondary endpoints are:

- Improvement in lower-back and leg pain VAS score at follow-up visits
- Improvement in ODI at follow-up visits
- Improvement in Quality of Life as measured by the SF-36 and EQ-5D at follow-up visits
- Serious adverse events
- Proportion of participants using narcotics
- Proportion of participants returning to work
- Proportion of participants relying on assistive ambulatory device
- Proportion of participants requiring revision/secondary surgical intervention

5. Study Enrollment and Withdrawal

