9.3.2. Analysis of the Secondary Endpoint(s)

Improvement in SF-36, EQ-5D, ODI, and VAS scores will be compared between groups using a repeated measure ANOVA (analysis of variance).

The occurrence rate of adverse events will be assessed using a Kaplan-Meier approach and a comparison of serious adverse event rates will be made using a chi-squared analysis.

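### For VAS, ODI, EQ-5D and SF-36, protocol 9.4.4 fixes LOCF, which carries the early device difference into later visits, and same-direction extreme fills, which understate the possible range when both arms have missing scores

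*Protocol*

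**What the plan says.** Protocol 9.4.4 (Missing Data) sets the rule for secondary endpoints: "In evaluating secondary endpoints, the following methods will be followed for including missing endpoint values". The three methods are "Last observation carried forward", "All missing data are worst possible response" and "All missing data are best possible response". None is marked as the main or as a sensitivity analysis. The two extreme fills apply to all missing data, so both arms are filled in the same direction.

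The rule covers every secondary endpoint in 4.2.2, including yes/no ones such as "Proportion of participants using narcotics". This point concerns only the four scores. Section 9.3.2 compares improvement in those scores between groups by a repeated-measures ANOVA. The objective in 3.2 is "to determine whether treatment with Tritanium or PEEK yields faster pain and quality of life improvement". Follow-up scores are taken at 6 weeks and 3, 6 and 12 months (6.3.2, 6.3.3).

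**The concern.** A question about speed of improvement is a question about how the device difference changes from visit to visit. LOCF places an earlier recovery score at a later visit, so it pulls the later difference towards the earlier one. An early advantage that has faded still shows at 12 months, and an advantage that appears late is understated. If one arm loses more participants while everyone is still recovering, LOCF can also create a difference.

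The extreme fills look like a check on this. When both arms have missing scores, though, filling both in the same direction partly or wholly cancels in the comparison. Two results that agree may be read as robustness that the data do not support.

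Missing scores are foreseeable. Participants may withdraw at any time (5.4.1), and 9.4.4 adds: "If 6-week radiographic endpoints cannot be obtained, the participant will be removed from the study".

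**Working it through.** **Inputs.** From the protocol: 20 participants (5.3); VAS from 0 to 100, higher worse (6.1.2.8); four follow-up visits. The protocol gives no dropout rate, SD, expected effect or allocation ratio, so it has no figure to reproduce. Assumed: 10 per arm, and all differences, means and missing counts below.

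**LOCF, equal dropout.** If a fraction f of each arm leaves after 6 weeks, the difference shown later is (1 - f) × late difference + f × 6-week difference.

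- Device advantage of 10, 6, 3, 0 points at the four visits, f = 0.2: 0.8 × 0 + 0.2 × 10 = 2.0 at 12 months (true 0).
- Same pattern, 7% leaving after each of the first three visits (weights 0.070, 0.0651, 0.0605; total 19.6%): 0.070 × 10 + 0.0651 × 6 + 0.0605 × 3 = 1.27. At 3.5% per visit it is 0.65.
- Late pattern 0, 3, 6, 10: all leaving after 6 weeks gives 0.8 × 10 = 8. The 7% spread gives 10 - (0.070 × 10 + 0.0651 × 7 + 0.0605 × 4) = 8.60 (true 10).
- A constant difference is unchanged: 0.8 × 10 + 0.2 × 10 = 10.

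**LOCF, unequal dropout.** No device difference at any visit, both arms improving from 45 to 30, 30% against 10% leaving after 6 weeks: (0.7 × 30 + 0.3 × 45) - (0.9 × 30 + 0.1 × 45) = 34.5 - 31.5 = 3 points.

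**Extreme fills.** Observed means 30 (Tritanium) and 40 (PEEK), difference -10. With 2 of 10 missing per arm:

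- All worst: (8 × 30 + 2 × 100)/10 - (8 × 40 + 2 × 100)/10 = 44 - 52 = -8.
- All best: 24 - 32 = -8.
- Opposite extremes: 24 - 52 = -28 and 44 - 32 = +12.

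In general, the same-direction pair has width 100 × |pT - pP|, where pT and pP are the missing proportions, and the possible range has width 100 × (pT + pP).

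| Missing, Tritanium/PEEK | Same-direction fills | Possible range |
|---|---|---|
| 1/1 | -9 and -9 | -19 to +1 |
| 2/1 | -12 and -2 | -22 to +8 |
| 2/2 | -8 and -8 | -28 to +12 |
| 2/0 | -16 and +4 | -16 to +4 |

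The pair falls short only when both arms have missing scores. With independent missingness p per participant, that probability is (1 - (1 - p)^10)^2, which is 16%, 42% and 80% at p = 5%, 10% and 20%.

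**The case against.** The detailed SAP is still to come (9.1). That would answer a silence, but 9.4.4 has already chosen the methods.

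The stronger objection is that LOCF may cost little. In 4000 simulated trials of the spread early pattern (10 per arm, SD 20, exchangeable correlation 0.5), the 12-month estimate was off by 1.37 with SD 8.86 under LOCF. A compound-symmetry mixed model was off by 0.02 with SD 9.06. The root mean squared errors are sqrt(1.37² + 8.86²) = 8.97 and 9.06. A second simulation gave 8.1 to 9.1 for LOCF against 9.0 to 9.9. So LOCF can be the more accurate estimator overall, despite its bias. This stands.

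Nor is inferential harm shown. In 8000 trials using a baseline-adjusted 12-month comparison on LOCF data (not the full repeated-measures ANOVA), rejection was 4.7% to 4.9% with no device difference and 5.6% to 5.7% in the fading pattern. A mixed model with heterogeneous Toeplitz covariance rejected in 6.0% at 12 months with no effect (1000 trials, standard error about 0.7 points, approximate degrees of freedom). The bias and SD figures above are for compound symmetry, not for that structure.

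The protocol also limits missingness. It has visit reminders and payment per visit (5.3), scores at an early termination visit if the participant is willing (6.3.4), and possible replacement of leavers at or before 6 weeks without imaging (9.4.1). And 9.4.4 never calls the extreme fills bounds.

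Three stronger readings are tempting but unsupported:

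- A reader might infer from 6.3.5 that out-of-window unscheduled visits cause missing scores. Those are extra visits; giving no survey there removes no score from a scheduled visit.
- A reader might infer that opposite extremes cure sign changes from chance imbalance. With 2 against 0 missing they return the same -16 and +4, and with both arms affected they change sign more readily.
- A reader might infer that LOCF invalidates the secondary results. With equal missingness and no device difference at any visit, it creates no expected difference.

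**Conclusion.** The point holds, at low to moderate importance. The fixed LOCF rule blurs the time course that 3.2 asks about: under assumed dropout of about 20%, a difference falling from 10 to 0 VAS points shows as about 1.3 to 2 points at 12 months. The same-direction fills miss much of the possible range when both arms have missing scores (-8 twice, against -28 to +12 at 2 of 10 per arm), and none of it when only one arm does.

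These sizes rest on assumed dropout, means and 10 per arm. Only the algebra is independent of them. The endpoints are secondary, and the case for change is fit to the objective at small cost, not a demonstrated error rate.

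**What to change.** - **9.3.2:** for the four scores, replace the repeated-measures ANOVA by a likelihood-based mixed model for repeated measures on observed data, with device, visit, device-by-visit and baseline score. Use small-sample degrees of freedom such as Kenward-Roger and a prespecified parsimonious covariance structure. Heterogeneous Toeplitz is one candidate: 7 parameters for four visits, against 10 unstructured. The choice matters with 20 participants. Compound symmetry rejected in 7.2% at 12 months when the true correlation was 0.7^lag, against 6.0% for Toeplitz.
- **9.4.4:** for these scores, drop LOCF or keep it only as a labelled sensitivity analysis. Add opposite-extreme fills by arm (worst Tritanium with best PEEK, and the reverse) as a labelled bound. The rules for the yes/no endpoints can stay.

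Deleting LOCF while keeping a classical ANOVA would not do, because that needs complete sets. At 5% or 10% missing per visit (assumed independent), only 20 × 0.95^4 = 16.3 or 20 × 0.90^4 = 13.1 participants would have all four follow-up scores.

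**Cost:** wording and some programming, with no new data. The model relies on missing-at-random and an assumed covariance. The bounds will often be inconclusive (40 VAS points wide at 2 of 10 missing per arm). Variance rises: the SD of the 12-month estimate was 2% to 8% larger than with LOCF in one set of simulations and about 9% to 14% larger in another.

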12.1. Ethical Standard

The principal investigator will ensure that this study is conducted in full conformity with Regulations for the Protection of Human Subjects of Research codified in 45 CFR Part 46, 21 CFR Part 50, 21 CFR Part 56.

12.2. Institutional Review Board

The protocol, informed consent form(s), recruitment materials, and all participant materials will be submitted to the Riverside Medical Center IRB for review and approval. Approval of both the protocol, consent form, and any recruitment materials must be obtained before any participant is enrolled. Any amendment to the protocol will require review and approval by the RMC IRB before the changes are implemented to the study. All changes to the consent form will be RMC IRB approved; a determination will be made regarding whether previously consented participants need to be re-consented.

12.3. Informed Consent Process

12.3.1. Consent Procedures and Documentation

Informed consent is a process that is initiated prior to the individual's agreeing to participate in the study and continues throughout the individual's study participation. Extensive discussion of risks and possible benefits of participation will be provided to the participants and their families, if present. Consent forms will be IRB-approved and the participant will be asked to read and review the document. The investigator will explain the research study to the participant and answer any questions that may arise. All participants will receive a verbal explanation in terms suited to their comprehension of the purposes, procedures, and potential risks of the study and of their rights as research participants. Participants will have the opportunity to carefully review the written consent form and ask questions prior to signing. The participants should have the opportunity to discuss the study with friends, family, or their physician, or think about it prior to

agreeing to participate. The participant will sign the informed consent document prior to any procedures being done specifically for the study. The participants may withdraw consent at any time throughout the course of the trial. A copy of the informed consent document will be given to the participants for their records. The rights and welfare of the participants will be protected by emphasizing to them that the quality of their medical care will not be adversely affected if they decline to participate in this study.

